 - Meningococcal vaccine (MenACYW conjugate vaccine or Menactra[®]): inject IM into the anterolateral area of the thigh, preferably the right thigh.
- 8) Observe the subject for 30 minutes and record any AEs in the source document.
- 9) Give the parent / guardian a diary card (DC2).
- 10) Remind the parent / guardian to expect a telephone call 8 days after Visit 2 and to bring back the diary card when they return for Visit 3 at a specified date and time.
- 11) Remind the parent / guardian to notify the site in case of an SAE.
- 12) Complete the relevant CRFs for this visit.

Telephone Call 2 (8 days [+2 days] after Visit 3)

Refer to steps in Telephone Call 1.

Visit 3 (30 [+21] days after Visit 2): Collection of Safety Information and Blood Sample

- 1) Collect and review the diary card (DC2) with the parent / guardian, including any AEs, medications, or therapy that occurred since vaccination. If an SAE, including an AESI, has occurred, follow the instructions in [Section 10](#) for reporting it.
- 2) Review temporary contraindications for blood sampling. Ensure the subject has not had any antibiotics within the previous 72 hours (3 days).
- 3) Collect 3 mL of blood (BL0002) (see [Section 7](#) for detailed instructions regarding the handling of blood samples).
- 4) Give the parent / guardian a memory aid to record SAE and MAAEs from Visit 3 until the 6-month follow-up phone call.
- 5) Remind the parent / guardian to notify the site in case of an SAE.
- 6) Complete the relevant CRFs for this visit and trial termination record.

Safety Follow-up Telephone Call 4 (180 [+30] days after Visit 4: Collection of SAEs

- 1) Ask the parent / guardian if the subject has experienced any SAE and / or MAAE since the last study visit. If an SAE, including an AESI, has occurred, follow the instructions in [Section 10](#) for reporting it.
- 2) Complete the relevant CRFs for this visit.

This call must be made by a qualified person.

A follow-up visit outside the scope of this study protocol can be arranged depending on the information recorded during the phone call.

Follow-up of subjects with Related AEs or with AEs That Led to Study/Vaccination Discontinuation:

A subject who experiences an AE (whether serious or non-serious) during the study must be followed until the condition resolves, becomes stable, or becomes chronic (even after the end of the subject's participation in the study) if *either* of the following is true:

- The AE is considered by the Investigator to be related to the product administered.
- The AE caused the discontinuation of the subject from the study or from vaccination.

5.1.5 Planned Study Calendar

The following dates are approximate. The actual dates may differ as, for example, the study will not start until all the appropriate regulatory and ethical approvals have been obtained.

Planned study period - FVFS (first visit, first subject) to LCLS (last contact, last subject):
04 October 2018 to 25 Aug 2023

Planned inclusion period - FVFS to FVLS (first visit, last subject): 05 October 2018 to 31 Jan 2022

Planned end of study: 25 Aug 2023

Planned date of final clinical study report: 1Q2024

The 6-month follow- up telephone call (TC 4 for Group 1 and Group 2 and TC3 for Group 3 and Group 4) of the last subject in all groups is considered to be the end of the study.

5.2 Enrollment and Retention of Study Population

5.2.1 Recruitment Procedures

Each site will be responsible for devising a recruitment plan for enrolling eligible subjects. Advertisements and other recruitment aids will be approved by Sanofi Pasteur and the site's IRB/IEC prior to use by the clinical site.

5.2.2 Informed Consent Procedures

Informed consent is the process by which a subject and / or parent / guardian voluntarily confirms his or her willingness to participate in a particular study. Informed consent must be obtained before any study procedures are performed. The process is documented by means of a written, signed, and dated ICF.

In accordance with GCP, prior to signing and dating the consent form, the parent / guardian must be informed by appropriate study personnel about all aspects of the study that are relevant to making the decision to participate, and must have sufficient time and opportunity to ask any questions.

The actual ICF used at each center may differ, depending on local regulations and IEC / IRB requirements. However, all versions must contain the standard information found in the sample ICF provided by the Sponsor. Any change to the content of the ICF must be approved by the Sponsor and the IEC / IRB prior to the form being used.

If new information becomes available that may be relevant to the parent's / guardian's willingness to continue participation in the study, this will be communicated to him / her in a timely manner. Such information will be provided via a revised ICF or an addendum to the original ICF.

Informed consent forms will be provided in duplicate, or a photocopy of the signed consent will be made. The original will be kept by the Investigator, and the copy will be kept by the subject's parent / guardian.

Documentation of the consent process should be recorded in the source documents.

5.2.3 Screening Criteria

There are no screening criteria other than the inclusion and exclusion criteria.

5.2.4 Inclusion Criteria

An individual must fulfill *all* of the following criteria to be eligible for study enrollment:

- 1) Aged 6 to 7 months (168 to 224 days)^a or 17 to 19 months on the day of the first visit^b
- 3) Informed consent form has been signed and dated by the parent(s) or other guardian and by an independent witness if required by local regulations
- 4) Subject and parent/guardian are able to attend all scheduled visits and to comply with all trial procedures
- 5) For subjects 6 to 7 months of age at enrollment (Group 1 and Group 2), documented history of having received 2 doses of DTaP, Hib, IPV, pneumococcal, hepatitis B (for children who received Pediarix® at 2 and 4 months of age, prior receipt of 3 doses of hepatitis B), and rotavirus (Rotateq®) vaccines
- 6) For subjects to be enrolled at 17 to 19 months of age (Group 3 and Group 4), documented history of having received all routine pediatric vaccines recommended by ACIP up to the age of enrollment

5.2.5 Exclusion Criteria

An individual fulfilling *any* of the following criteria is to be excluded from study enrollment:

- 1) Participation at the time of study enrollment or in the 4 weeks preceding the first trial vaccination or planned participation during the present trial period in another clinical trial investigating a vaccine, drug, medical device, or medical procedure

^a At Visit 1, subjects must be at least 24 weeks of age (168 days, the minimum age for the final dose of hepatitis B vaccine in the vaccine series), and no more than 32 weeks of age (224 days, the maximum age for the 3rd dose of rotavirus vaccine administration).

^b “6 to 7 months” means from the 6th month after birth to the day before the 8th month after birth. “168 to 224 days” means from the 168th day after birth to the day before the 225th day after birth. “17 to 19 months” means from the 17th month after birth to the day before the 20th month after birth.

- 2) Receipt of any vaccine in the 4 weeks preceding the first trial vaccination or planned receipt of any vaccine in the 4 weeks before and / or following any trial vaccination except for influenza vaccination, which may be received at least 2 weeks before or 2 weeks after any study vaccination. This exception includes monovalent pandemic influenza vaccines and multivalent influenza vaccines
- 3) Previous vaccination against meningococcal disease with either the trial vaccine or another vaccine (i.e., mono- or polyvalent, PS, or conjugate meningococcal vaccine containing serogroups A, C, Y, or W; or meningococcal B serogroup-containing vaccine)
- 4) For subjects to be enrolled at 6 to 7 months of age (Group 1 and Group 2), prior receipt of more than 2 doses of rotavirus vaccine (Rotateq), DTaP, Hib, IPV, pneumococcal, hepatitis B; for children who received Pediarix® at 2 and 4 months of age, prior receipt of more than 3 doses of hepatitis B vaccine
- 5) For subjects to be enrolled at 6 to 7 months of age (Group 1 and Group 2), receipt of 2 doses of rotavirus vaccine, Rotarix® at 2 and 4 months of age
- 6) Receipt of immune globulins, blood, or blood-derived products in the past 3 months
- 7) Known or suspected congenital or acquired immunodeficiency or receipt of immunosuppressive therapy, such as anti-cancer chemotherapy or radiation therapy within the preceding 6 months; or long-term systemic corticosteroid therapy (prednisone or equivalent for more than 2 consecutive weeks) within the past 3 months
- 8) Family history of congenital or hereditary immunodeficiency, until the immune competence of the potential vaccine recipient is demonstrated
- 9) Individuals with blood dyscrasias, leukemia, lymphoma of any type, or other malignant neoplasms affecting the bone marrow or lymphatic systems
- 10) Individuals with active tuberculosis
- 11) History of any *Neisseria meningitidis* infection, confirmed either clinically, serologically, or microbiologically
- 12) History of diphtheria, tetanus, pertussis, poliomyelitis, hepatitis B, hepatitis A, measles, mumps, rubella, varicella; and of *Haemophilus influenzae* type b, *Streptococcus pneumoniae*, and /or rotavirus infection or disease
- 13) At high risk for meningococcal infection during the trial (specifically, but not limited to, subjects with persistent complement deficiency, with anatomic or functional asplenia, or subjects travelling to countries with high endemic or epidemic disease)
- 14) History of intussusception

- 15) History of any neurologic disorders, including any seizures and progressive neurologic disorders
- 16) History of Arthus-type hypersensitivity reaction after a previous dose of tetanus toxoid-containing vaccine
- 17) History of Guillain-Barré syndrome
- 18) Known systemic hypersensitivity to any of the vaccine components or to latex, or history of a life-threatening reaction to the vaccine(s) used in the trial or to a vaccine containing any of the same substances, including neomycin, gelatin, and yeast^a
- 19) Verbal report of thrombocytopenia contraindicating intramuscular vaccination in the investigator's opinion
- 20) Bleeding disorder, or receipt of anticoagulants in the 3 weeks preceding inclusion, contraindicating intramuscular vaccination in the investigator's opinion
- 21) Receipt of oral or injectable antibiotic therapy within 72 hours prior to the first blood draw
- 22) Chronic illness that, in the opinion of the investigator, is at a stage where it might interfere with trial conduct or completion^b
- 23) Any condition which, in the opinion of the investigator, might interfere with the evaluation of the study objectives
- 24) Moderate or severe acute illness/infection (according to investigator judgment) on the day of vaccination or febrile illness (temperature $\geq 38.0^{\circ}\text{C}$ [$\geq 100.4^{\circ}\text{F}$]). A prospective subject should not be included in the study until the condition has resolved or the febrile event has subsided
- 25) Identified as a natural or adopted child of the investigator or employee with direct involvement in the proposed study

If the subject has a primary physician who is not the Investigator, the site must contact this physician with the parent's / guardian's consent to inform him / her of the subject's participation in the study. In addition, the site should ask this primary physician to verify exclusion criteria relating to previous therapies, such as receipt of blood products or previous vaccines.

5.2.6 Medical History

Prior to enrollment, subjects will be assessed for pre-existing conditions and illnesses, both past and ongoing. Any such conditions will be documented in the source document. Significant

^a The components of all study vaccines are listed in [Section 6.1.1.1](#) and in the Investigator's Brochure

^b Chronic illness may include, but is not limited to, cardiac disorders, renal disorders, auto-immune disorders, diabetes, psychomotor diseases, and known congenital or genetic diseases.

(clinically relevant) medical history (reported as diagnosis) including conditions/illnesses for which the subject is or has been followed by a physician or conditions/illnesses that could resume during the course of the study or lead to an SAE or to a repetitive outpatient care will be collected in the CRB. The significant medical history section of the CRB contains a core list of body systems and disorders that could be used to prompt comprehensive reporting, as well as space for the reporting of specific conditions and illnesses.

For each condition, the data collected will be limited to:

- Diagnosis (this is preferable to reporting signs and symptoms)
- Presence or absence of the condition at enrollment

The reporting of signs and symptoms in lieu of a diagnosis is strongly discouraged.

Dates, medications, and body systems are not to be recorded, and the information collected will not be coded. Its purpose is to assist in the later interpretation of safety data collected during the study.

5.2.7 Contraindications for Subsequent Vaccinations

5.2.7.1 Temporary Contraindications

Should a subject experience one of the conditions listed below, the Investigator will postpone further vaccination until the condition is resolved. Postponement must still be within the timeframe for vaccination indicated in the Table of Study Procedures.

- Febrile illness (temperature $\geq 38.0^{\circ}\text{C}$ [$\geq 100.4^{\circ}\text{F}$]) or moderate or severe acute illness / infection on the day of vaccination, according to Investigator judgment.
- Receipt of any vaccine (other than the study vaccines) in the 4 weeks preceding the first study vaccination or planned receipt of any vaccine in the 4 weeks before and / or following any study vaccination except for influenza vaccination, which may be received at least 2 weeks before or 2 weeks after study vaccination. This exception includes monovalent pandemic influenza vaccines and multivalent influenza vaccines.

The following is a temporary contraindication to blood draw:

- Receipt of oral or injected antibiotic therapy within the 72 hours (3 days) prior to a study blood draw. Note: if a subject receives oral or injectable antibiotic therapy within 3 days prior to a blood draw, the investigator will postpone that blood draw until it has been 3 days since the subject last received oral or injectable antibiotic therapy. Postponement must still be within the timeframe for blood draw. If postponement would result in the sample collection falling outside of this timeframe, the blood sample should be collected without postponement, and it should be documented appropriately that the sample was taken less than 3 days after stopping antibiotic treatment.

5.2.7.2 Definitive Contraindications

Prior to vaccination, check the complete list of contraindications for each individual vaccine to be administered. For the licensed vaccines refer to the individual current package inserts. For MenACYW conjugate vaccine refer to the Investigator's Brochure.

Should a subject experience an anaphylactic or other significant allergic reaction to the previous dose of vaccine(s), the Investigator will discontinue vaccination.

The following AEs constitute absolute contraindications to subsequent vaccination with any of the study vaccines. If a subject should experience any of these events during the study, that subject is not to receive any additional study vaccines but should continue in the study and be followed up for safety only as per protocol up to 6 months after the last vaccinations received.

Meningococcal vaccines (MenACYW conjugate vaccine, MENVEO® or Menactra®):

- 1) History of Guillain-Barre syndrome within 6 weeks after vaccination with a tetanus toxoid-containing vaccine.
- 2) History of an Arthus-like hypersensitivity reaction after vaccination with a tetanus toxoid-containing vaccine.
- 3) Severe allergic reaction (e.g., anaphylaxis) after a previous dose of meningococcal capsular polysaccharide-, diphtheria toxoid- or CRM₁₉₇ –containing vaccines or to any component of meningococcal vaccines.

M-M-R®II (measles, mumps, and rubella vaccine):

- 4) Hypersensitivity to any component of the vaccine, including gelatin.
- 5) Anaphylactic or anaphylactoid reactions to neomycin.
- 6) Patients receiving immunosuppressive therapy. This contraindication does not apply to patients who are receiving corticosteroids as replacement therapy, e.g., for Addison's disease.
- 7) Individuals with newly diagnosed (after inclusion in the study) blood dyscrasias, leukemia, lymphomas of any type, or other malignant neoplasms affecting the bone marrow or lymphatic systems.
- 8) Newly diagnosed (after inclusion in the study) primary and acquired immunodeficiency states, including patients who are immunosuppressed in association with acquired immune deficiency syndrome (AIDS) or other clinical manifestations of infection with human immunodeficiency viruses; cellular immune deficiencies; and hypogammaglobulinemic and dysgammaglobulinemic states.
- 9) Individuals with family members newly diagnosed (after a subject's inclusion in the study) with congenital or hereditary immunodeficiency, unless immune competence of the potential vaccine recipient has been demonstrated.

Varivax® (varicella vaccine):

- 10) History of severe allergic reaction to any component of the vaccine (including neomycin and gelatin) or to a previous dose of varicella vaccine.
- 11) Newly diagnosed (after inclusion in the study) primary or acquired immunodeficiency states, leukemia, lymphoma or other malignant neoplasms affecting the bone marrow or lymphatic system, AIDS, or other clinical manifestations of infection with human immunodeficiency virus (HIV).
- 12) Individuals receiving immunosuppressive therapy, including individuals receiving immunosuppressive doses of corticosteroids. A substantially immunosuppressive steroid dose is considered to be \geq 2 weeks of daily receipt of 20 mg or 2 mg/kg body weight of prednisone or equivalent. For further information on contraindications to Varivax vaccination in persons receiving immunosuppressive therapies, consult the General Best Practices Guidelines for Immunization, the Recommendations of the Advisory Committee on Immunization Practices (ACIP), and the Pinkbook [\(39\)](#) [\(40\)](#) [\(41\)](#)
- 13) Active untreated tuberculosis.

Subjects with a definitive contraindication will continue to be followed up for the study-defined safety and immunogenicity assessments, as applicable.

In the event of a local or national immunization program with a pandemic influenza vaccine, subjects who receive pandemic influenza vaccine at any time during the study will not be withdrawn from the study.

5.2.7.3 Warnings and Precautions to Vaccination

Prior to vaccination, check the warnings and precautions for each individual vaccine to be administered. For the licensed vaccines, refer to the individual package inserts. For MenACYW conjugate vaccine, refer to the Investigator's Brochure.

5.2.8 Conditions for Withdrawal

Parents / guardians will be informed that they have the right to withdraw their child from the study at any time.

A subject may be withdrawn from the study:

- At the discretion of the Investigator or Sponsor due to safety concerns or significant non-compliance with the protocol (based on the Investigator's judgment), without the subject's permission (withdrawal)
- At the request of the parent / guardian (dropout)

The reason for a withdrawal or dropout should be clearly documented in the source documents and on the CRB.

The Investigator must determine whether voluntary withdrawal is due to safety concerns (in which case, the reason for discontinuation will be noted as “Adverse Event”) or for another reason.

Withdrawn subjects will not be replaced.

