5.2.10 Classification of Subjects Who Discontinue the Study

For any subject who discontinues the study prior to completion, the most significant reason for early termination will be checked in the CRB. Reasons are listed below from the most significant to the least significant (refer to the CRB completion instructions for additional details and examples):

Adverse Event	To be used when the subject is permanently terminated from the study because of an AE (including an SAE), as defined in Section 9.3.2.1 . This category also applies if the subject experiences a definitive contraindication that is an SAE or AE.
Lost to Follow-up	To be used when the subject cannot be found or contacted in spite of efforts to locate him/her before the date of his/her planned last visit, as outlined in Section 5.2.9 . The certified letter was sent by the investigator and returned unsigned, and the parent/guardian did not give any other news and did not come to any following visit.
Protocol Deviation	To be used: 
In case of significant noncompliance with the protocol (e.g., deviation of the Inclusion / Exclusion criteria, non-compliance with time windows, blood sampling or vaccination refusal, missed injection/treatment, or error in the vaccine/treatment administration).If the subject experiences a definitive contraindication that is a protocol deviation.The parent/guardian signed the certified letter sent by the investigator but did not give any other news and did not come to any following visit.
Withdrawal by Parent / Guardian	To be used: 
When the subject or parent/guardian indicated unwillingness to continue in the studyWhen the parent/guardian made the decision to discontinue participation in the study for any personal reason other than an SAE/AE (e.g., subject is relocating, inform consent withdrawal, etc.)

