9.3.2 Safety

9.3.2.1 Safety Definitions

The following definitions are taken from the ICH E2A Guideline for Clinical Safety Data Management: Definitions and Standards for Expedited Reporting.

Adverse Event (AE):

An AE is any untoward medical occurrence in a patient or in a clinical investigation subject administered a medicinal product and which does not necessarily have a causal relationship with this treatment. An AE can therefore be any unfavorable and unintended sign (including an abnormal laboratory finding, for example), symptom or disease temporally associated with the use of a medicinal product, whether or not considered related to the medicinal product.

Therefore an AE may be:

- A new illness

- The worsening of a pre-existing condition
- An effect of the vaccination, including the comparator
- A combination of the above

All AEs include serious and non-serious AEs.

Surgical procedures are not AEs; they are the actions taken to treat a medical condition. It is the condition leading to the action taken that is the AE (if it occurs during the study period).

Pre-existing medical conditions are not to be reported as AEs. However, if a pre-existing medical condition worsens following study interventions in frequency or intensity, or if according to the Investigator there is a change in its clinical significance, this change should be reported as an AE (exacerbation). This applies equally to recurring episodes of pre-existing conditions (e.g., asthma) if the frequency or intensity increases post-vaccination.

Serious Adverse Event (SAE):

Serious and *severe* are not synonymous. The term *severe* is often used to describe the intensity of a specific event as corresponding to Grade 3. This is not the same as *serious* which is based on subject / event outcome or action criteria usually associated with events that pose a threat to a subject's life or functioning. Seriousness, not severity, serves as a guide for defining regulatory reporting obligations.

An SAE is any untoward medical occurrence that at any dose

- Results in death
- Is life-threatening^a
- Requires inpatient hospitalization or prolongation of existing hospitalization^b
- Results in persistent or significant disability / incapacity^c
- Is a congenital anomaly / birth defect
- Is an important medical event (IME)

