4.4.2.5.5 AEs Leading to Study Discontinuation

This information will be summarized as collected. A flag is available in the clinical database for all AEs in order to identify AEs leading to discontinuation before the end of active phase.

In general, the items that are counted are:

- Disposition table: A participant who, on the “Completion at End of Study” form question “What was the participant's status?” has “Adverse Event” checked.
- Safety overview table: A participant who has either on the “Completion at End of Study” form, question “What was the participant's status?” has “Adverse Event” checked or lists a solicited AE that has “Caused Study Termination” checked that is at least Grade 1 or an unsolicited AE that has “Caused Study Discontinuation” checked that is at least Grade 1 or missing and is within the time period indicated.
- System Organ Class (SOC)/Preferred Term (PT) table: A solicited AE that has “Caused Study Termination” checked that is at least Grade 1 or an unsolicited AE that has “Caused Study Discontinuation” checked that is at least Grade 1 or missing and is within the time period indicated.

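### Protocol 5.2.8 and 5.2.10 give different reason codes to a voluntary withdrawal over safety worry with no AE, so two SAP tables can count it as AE-led

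*Protocol*

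**What the plan says.** **Coding instruction, Protocol 5.2.8.** "The Investigator must determine whether voluntary withdrawal is due to safety concerns (in which case, the reason for discontinuation will be noted as". The code named at that point is 'Adverse Event'; the alternative is any other cause. The trigger is a safety concern, and the sentence is limited to voluntary withdrawal. Removal by the Investigator or Sponsor is a separate route in the same section ("At the discretion of the Investigator or Sponsor due to safety concerns or significant non-compliance with the protocol"), and no reason code is stated there for it.

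**Classification list, Protocol 5.2.10.** The 'Adverse Event' reason carries this rule: "To be used when the subject is permanently terminated from the study because of an AE (including an SAE), as defined in". The cross-reference is to Section 9.3.2.1. The same reason also covers a definitive contraindication that is an AE or SAE. 'Withdrawal by Parent / Guardian' covers, among other cases, a parent who "made the decision to discontinue participation in the study for any personal reason other than an SAE/AE".

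**Definition, Protocol 9.3.2.1.** "An AE is any untoward medical occurrence in a patient or in a clinical investigation subject administered a medicinal product".

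**Counting rules, SAP 4.4.2.5.5.**
- "Disposition table: A participant who, on the “Completion at End of Study” form question “What was the participant's status?” has “Adverse Event” checked".
- For the safety overview, that same status box is enough by itself; an AE flagged as the cause is the other way in.
- The SOC/PT table counts only AE records flagged as the cause.

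**Follow-up, Protocol 5.2.11.** After termination for an AE, the site completes all scheduled safety follow-ups. After voluntary withdrawal, it attempts the 6-month contact unless the family has declined further contact.

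**The concern.** A safety concern is not the same thing as an AE. A parent can come to fear the vaccine and withdraw a child who has had no untoward occurrence. For that child the protocol gives two answers, and the SAP then takes the end-of-study status box at face value in two of its three tables. The number of subjects discontinued because of an AE is read closely in any vaccine safety summary. It is usually small, so a few children with no event behind the code could change it visibly. The tables could also disagree with one another, and the site could apply a different follow-up rule depending on which section it read.

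**Working it through.** The point is textual; the plan states no figure to reproduce. I took one case, a voluntary withdrawal by a parent worried about safety with no AE in the child, through each rule.

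| Step | Rule | Result for this child |
|---|---|---|
| Is there an AE? | Protocol 9.3.2.1 | No: worry in the parent is not a medical occurrence in the child |
| Reason code | Protocol 5.2.8 | 'Adverse Event' |
| Reason code | Protocol 5.2.10 | 'Withdrawal by Parent / Guardian' |
| Follow-up if coded 'Adverse Event' | Protocol 5.2.11 | All scheduled safety follow-ups |
| Follow-up if coded as parental withdrawal | Protocol 5.2.11 | Attempted 6-month contact unless declined |
| Disposition table, if status is 'Adverse Event' | SAP 4.4.2.5.5 | Counted (status box alone) |
| Safety overview, if status is 'Adverse Event' | SAP 4.4.2.5.5 | Counted (status box or AE flag) |
| SOC/PT table | SAP 4.4.2.5.5 | Not counted (no AE record) |

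The ranking in 5.2.10 from most to least significant reason does not remove the conflict. It puts 'Adverse Event' first, so a site that thinks both codes apply is led to that one.

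**Scale.** Inputs: 435 enrolled in each of Groups 1 and 2, and 100 in each of Groups 3 and 4 (Protocol synopsis, planned sample size). The number of no-event withdrawals coded 'Adverse Event', x, is not given and is assumed here. Rate = x/n, with Clopper-Pearson 95% limits, the method the SAP names for safety proportions. The table assumes no true AE-led discontinuations.

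| x (assumed) | n = 435 | n = 100 |
|---|---|---|
| 0 | 0% (0 to 0.84) | 0% (0 to 3.62) |
| 1 | 0.23% (0.01 to 1.27) | 1.0% (0.03 to 5.45) |
| 5 | 1.15% (0.37 to 2.66) | 5.0% (1.64 to 11.28) |
| 10 | 2.30% (1.11 to 4.19) | 10.0% (4.90 to 17.62) |

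Each such child adds 1/435 = 0.23 points, or 1/100 = 1.0 point. Safety is analysed on the safety analysis sets, so actual denominators may be somewhat below the enrolled numbers.

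**The case against.** The best reply is that 5.2.10 is the operative classification. It gives precise definitions, refers to 9.3.2.1, and sends sites to CRB completion instructions that are not among the documents. Read with it, 'safety concerns' in 5.2.8 may be loose shorthand for an AE, and sites may have been told so. That is possible, and it is why the miscount is conditional. But the protocol also uses the phrase more widely, for example for the sponsor's programme-level safety review (Protocol 3 and 5.5), and 5.2.8 as written asks for no event.

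Several stronger readings are tempting and do not hold:

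- *Every withdrawal for safety concerns is coded 'Adverse Event'.* The sentence covers voluntary withdrawal only.
- *Worried parents are counted as AE-led discontinuations.* They can be. It takes a child with no event and a site that applies 5.2.8 literally.
- *The safety endpoint itself mixes reactions with worry.* The endpoints in Protocol 9.3.2.2 ask whether a recorded event led to termination. The SAP has a flag on AE records "in order to identify AEs leading to discontinuation before the end of active phase", and the SOC/PT table relies on AE records. Only participant-level rows in two tables are exposed.
- *The tables cannot be reconciled.* Each counting rule is stated, so status-only children can be found as the difference. Protocol 11.2 and 11.3 and SAP 5.6 provide consistency checks and data review before lock, although none names this check.
- *Pandemic fear makes this common.* Nothing says that fear of clinic visits is a safety concern in the sense of 5.2.8, and SAP 5.1.4.1 already summarises early terminations due to COVID-19 and lists the subjects affected.

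It is also fair to say that the overview's either-or rule has a use: it keeps a true AE withdrawal whose causal flag was missed. Requiring a flagged AE for that table could lose such a child.

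**Conclusion.** The conflict stands for one case: voluntary withdrawal over a safety concern with no AE. Under 5.2.8 such a child can appear as an AE-led discontinuation in the disposition and safety overview tables and be absent from the SOC/PT table, and the applicable follow-up rule in 5.2.11 changes with the code. The error runs towards over-counting AE-led discontinuations, not hiding them. The size per child is fixed by group size; the total is unknown because the documents give no expected number. Safety is descriptive here, with no hypothesis tested, and the primary non-inferiority analysis and its power are untouched. This is a contradiction between two coding rules that is worth correcting because the correction is nearly free. It is not a fault in the trial's design.

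**What to change.** 1. **Protocol 5.2.8.** Make the 'Adverse Event' reason apply to a voluntary withdrawal due to an AE as defined in 9.3.2.1, in line with 5.2.10. State that a safety concern without an AE is coded 'Withdrawal by Parent / Guardian', with the concern recorded in the source documents and the CRB. The follow-up rule in 5.2.11 then follows from a single code.
2. **SAP 4.4.2.5.5.** Leave the overview rule (status box or AE flag) as it is.
3. **Before database lock.** Add an edit check that queries every 'Adverse Event' completion status with no AE record flagged as the cause. The site then either supplies the missing AE or flag, or corrects the reason code.

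Cost: a short change to one sentence in the protocol and one edit check. No new data are collected, and no hypothesis, analysis set or sample size changes.
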